## 10.4. Appendix 4: Reporting Standards for Missing Data

### 10.4.1. Premature Withdrawals

Element	Reporting Detail
General	
 
As specified in the protocol (Section 5.3), a participant is considered to have completed the study if he/she has completed up to the end of session 2 of the study.
 
If a participant withdraws before the end of session 2 they will be encouraged to return for a follow-up visit as per the schedule of activities.
 
If a participant withdraws before the end of session 2 their data may still be used for analysis, depending on how much data is available. If there is insufficient data for analysis, at the discretion of the study team, this participant will be replaced.
 
The end of the study is defined as the date of the last visit of the last participant in the Study (e.g. the second follow up session for the last participant).
 
All available data from participants who were withdrawn from the study will be listed.
 

### 10.4.2. Handling of Missing Data

Element	Reporting Detail
General	
 
Missing data occurs when any requested data is not provided, leading to blank fields on the collection instrument:
 
These data will be indicated by the use of a “blank” in subject listing displays. Unless all data for a specific visit are missing in which case the data is excluded from the table.
 
Answers such as “Not applicable” and “Not evaluable” are not considered to be missing data and should be displayed as such.
 
 
For Biomarkers, the following will be applied:
 
 
If any value is not quantified and the numeric result is absent as the value is below the lower limit of quantification, then values will be imputed as half of the LLQ.
 
If any value is below the lower limit of quantification but the numeric result is present, then the numeric values will be used in all displays.
 
If any value is above ULQ, such values will be omitted from summaries/figures even if the numeric result is present. These values will only be listed.
 
Numeric results of samples which are “Plate failed QC” and “CV>20%” will be used in all displays.
 
Appropriate footnotes will be provided in Tables and Summaries to indicate that <LLQ, CV>20% and Plate Failed Samples have been used.
 
The diluted samples of the biomarkers whose value is >ULQ will be re-run and the new reported values will be used in the final analysis.
 

Outliers	
 
Any participants excluded from the summaries and/or statistical analyses will be documented along with the reason for exclusion in the clinical study report.
 

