### 7.2.2. Summary Measure

Absolute values and change from baseline of soluble and cellular inflammatory biomarkers across the time course.

Note: In the Interim Analysis, for the biomarkers from skin blister fluid, values will be averaged across arms (left and right) for each participant. These averaged values will be used in tables and figures.

If one of the values is not collected or is missing, then the single value present in the data will be used in tables and figures. Appropriate footnotes will be provided to reflect data are not an average value.

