**10.8. Appendix 8: Example Mock Shells for Data Displays**

Example: BIO\_T1  
 Protocol: 207654  
 Population: Safety

Page 1 of n

Table 2.1  
 Summary of Primary Soluble Inflammatory Mediators in Blood

Treatment: LPS x.x ng/kg (N=xx)  
 Biomarker: xxxx (units)

Visit	Planned Relative Time	n	Mean	SD	Median	Min.	Max.	%CVb
SESSION 1 DAY 1	PRE BLISTER INDUCTION	x	x.xxx	x.xxxx	x.xxx	x.xx	x.xx	xx%
SESSION 1 DAY 2	PRE FLUID SAMPLING	x	x.xxx	x.xxxx	x.xxx	x.xx	x.xx	xx%
SESSION 1 DAY 3	PRE FLUID SAMPLING	x	x.xxx	x.xxxx	x.xxx	x.xx	x.xx	xx%
SESSION 2 DAY 1	PRE BLISTER INDUCTION	x	x.xxx	x.xxxx	x.xxx	x.xx	x.xx	xx%
SESSION 2 DAY 1	-5 MIN	x	x.xxx	x.xxxx	x.xxx	x.xx	x.xx	xx%

Note: Biomarker xxxx includes <LLQ values, Biomarker yyyy includes CV>20% values, Biomarker zzzz includes Plate failed QC values (only if applicable).

Note: Values recorded as '<LLQ' have been imputed as LLQ/2 (only if applicable).

[figure not shown]
Repeat for all treatments and biomarkers

For all Summaries of Change from baseline, provide the footnote as below:

Note: Session x Day x is considered as Baseline.

Example: BIO\_F1  
 Protocol: 207654  
 Population: Safety

Figure 2.1  
 Individual Plot of Primary Soluble Inflammatory Mediators in Blood Over Time

S1D1=Session 1 Day 1, S1D2=Session 1 Day 2, S1D3=Session 1 Day 3, S2D1=Session 2 Day 1, S2D2=Session 2 Day 2, S2D3=Session 2 Day 3, PBI=Pre Blister Induction, PFS=Pre Fluid Sampling

Note: Biomarker xxxx includes <LLQ values, Biomarker yyyy includes CV>20% values, Biomarker zzzz includes Plate failed QC values (only if applicable).

Note: Values recorded as '<LLQ' have been imputed as LLQ/2 (only if applicable).

[figure not shown]
Repeat for all available treatments and biomarkers.

For Individual Plots of Change from baseline, provide the footnote as below:

Note: Session x Day x is considered as Baseline.

Example: BIO\_F2  
 Protocol: 207654  
 Population: Safety

Figure 2.3  
 Mean (+/- SD) Plot of Primary Soluble Inflammatory Mediators in Blood Over Time

[figure not shown]
S1D1=Session 1 Day 1, S1D2=Session 1 Day 2, S1D3=Session 1 Day 3, S2D1=Session 2 Day 1, S2D2=Session 2 Day 2, S2D3=Session 2 Day 3, PBI=Pre Blister Induction, PFS=Pre Fluid Sampling

Note: Biomarker xxx includes <LLQ values, Biomarker yyy includes CV>20% values, Biomarker zzzz includes Plate failed QC values (only if applicable).  
 Note: Values recorded as '<LLQ' have been imputed as LLQ/2 (only if applicable).  

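### Two different rules for below-LLQ biomarker results (LLQ/2 without a number, the reported number with one) can reverse the displayed direction of a change when both values lie below LLQ

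*SAP*

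**What the plan says.** SAP 10.4.2 (Handling of Missing Data) gives two instructions for biomarker results below LLQ.

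- No number available, for the reason that "the value is below the lower limit of quantification, then values will be imputed as half of the LLQ".
- Number available: "below the lower limit of quantification but the numeric result is present, then the numeric values will be used in all displays".

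Both are worded value by value, so both can apply within one biomarker and one participant. The section adds a disclosure: "Appropriate footnotes will be provided in Tables and Summaries to indicate that" below-LLQ results were used. The mock table BIO_T1 in SAP 10.8 carries a note beginning "Values recorded as '<LLQ' have been imputed as LLQ/2".

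These values enter the main summaries. For secondary biomarkers SAP 7.2.2 specifies "Absolute values and change from baseline of soluble and cellular inflammatory biomarkers across the time course", and SAP 7.1.2 does the same for the primary ones. SAP 3.2 also uses increases from baseline to decide whether Part II opens. For urinary tetranor PGDM that limit is a ratio, 1.3x.

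**The concern.** Below LLQ is one assay state, yet it gets two treatments that do not preserve order. A sample too low to yield a number is shown at 0.5 x LLQ. A sample that yields 0.2 or 0.3 x LLQ is shown at that lower figure. If the first truly contains less analyte, the display ranks the pair backwards, and the change from baseline takes the wrong sign.

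The plan itself expects low levels. Protocol 3.2 and 9.7.2 describe prostaglandin metabolites as very low in healthy people, and SAP 3.2 provides for biomarkers that are undetectable throughout Part I. Only four participants per agent are planned at the selected dose in Part I, so one reversed participant is a quarter of the group. The study's purpose is to describe direction, time course and size of response, so a wrong sign in a display matters even without a formal test.

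**Working it through.** The plan states no figure that depends on this rule, so there is nothing to reproduce. The check is algebra, then an illustration on stated assumptions. Set LLQ = 1.

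**Rule as written (SAP 10.4.2).** Displayed value = 0.5 if there is no number; = x if there is one.

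**Assumption, not in the documents.** A number is missing when the true level is below a cutoff c, so no-number samples are the lowest.

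**When the order reverses.** A no-number sample (0.5) is shown above a numbered one only if that number is below 0.5. Hence c must be below 0.5, and both members of the pair must lie below LLQ.

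| Baseline to post (true) | True ratio | Displayed | Displayed ratio |
|---|---|---|---|
| 0.1 (no number) to 0.3 | 3.0 | 0.5 to 0.3 | 0.6 |
| 0.3 to 0.1 (no number) | 0.33 | 0.3 to 0.5 | 1.67 |
| 0.1 (no number) to 0.6 | 6.0 | 0.5 to 0.6 | 1.2 |
| 0.1 (no number) to 2 | 20 | 0.5 to 2 | 4.0 |

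The first two rows reverse. The last two are attenuated but keep their direction. With LLQ/2 for all, the first three rows display as no change and the fourth is the same as now.

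**How often.** Assume log-normal levels with median m and log SD 0.6, and a true 1.5-fold rise in everyone. A rise is shown as a fall when x < c, 1.5x ≥ c and 1.5x < 0.5, so

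P = Φ[ln(min(c, 0.5/1.5)/m)/0.6] − Φ[ln((c/1.5)/m)/0.6], and P = 0 for c ≥ 0.5.

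Example, c = 0.2 and m = 0.3: Φ(−0.676) − Φ(−1.351) = 0.250 − 0.088 = 0.16.

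| Median (x LLQ) | c = 0.05 | 0.1 | 0.2 | 0.3 | 0.4 | 0.5 |
|---|---|---|---|---|---|---|
| 0.15 | 2.7% | 16% | 26% | 19% | 7.7% | 0 |
| 0.3 | 0.1% | 2.7% | 16% | 25% | 15% | 0 |
| 0.5 | 0.0% | 0.3% | 5% | 13% | 10% | 0 |

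With four participants, the chance that at least one is shown falling is 1 − (1 − P)^4: 50% at P = 0.16 and 68% at P = 0.25.

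**Mean change, c = 0.2 (x LLQ).** True mean change is 0.5·m·exp(0.6²/2).

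| Median | True | SAP rule | LLQ/2 for all | Shown as exactly zero under LLQ/2 for all |
|---|---|---|---|---|
| 0.15 | 0.090 | −0.017 | 0.004 | 99% |
| 0.3 | 0.180 | 0.122 | 0.062 | 91% |
| 0.5 | 0.299 | 0.282 | 0.223 | 68% |

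LLQ/2 for all reverses nobody, but its mean is further from the truth than the SAP rule in the second and third rows.

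**PGDM ratio (SAP 3.2), if imputed values feed it.**

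- No-number baseline: the display stays under 1.3x whenever the maximum post value is below 0.5 × 1.3 = 0.65. A change from 0.2 to 0.64 is truly 3.2x but displays as 1.28x.
- Numbered baseline below 0.5/1.3 = 0.38, followed by one no-number void: displays at least 1.3x although PGDM fell. PGDM is listed as a concentration (SAP 10.3.3), and LPS participants receive saline at 250 mL/hr for 12 hours around dosing (Protocol 7.1), so such a fall is conceivable.

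**Primary cytokines.** Protocol 10.1 cites at least 42-fold (TNF-alpha) and 100-fold (IL-6) rises at 1 ng/kg (10 EU/ng). With a 42-fold rise in the model above, 0.0% are shown falling at medians from 0.15 to 1.0 and cutoffs from 0.05 to 0.5. The 50 pg/mL Part II limits are absolute, and the imputation error in any one value is below LLQ/2.

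**The case against.** The strongest reply is that the reversal is conditional. The documents give no LLQ, do not say why some below-LLQ results have a number, and do not say how often the two kinds mix. If an assay always reports a number, never does, or reports none under LLQ/2, nothing reverses. This stands. A reader might infer that the lowest samples are always ranked above higher ones; the text supports only that they can be.

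Three other strong readings also fail.

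- A reader might infer that every biomarker's change from baseline is exposed. Blister volume and the TruCulture results have no change-from-baseline table (SAP 10.7.4). Leukocyte counts in healthy volunteers are not plausibly near an LLQ. The blister baseline is an already inflamed 24-hour blister (SAP 5.2).
- A reader might infer that the BIO_T1 note is false. It can be read as covering only results recorded as text without a number, and it then agrees with 10.4.2. It is ambiguous, because mock listing BIO_L1 also uses <LLQ as a comment beside a result.
- A reader might infer that the PGDM criterion could open Part II by itself. The three LPS criteria are joined by AND, so TNF-alpha and IL-6 must also be under their limits.

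It is also fair that this SAP version covers only dose escalation and the interim, that interim outputs are descriptive, and that footnotes, listings and individual plots would let a careful reader find affected points. These safeguards disclose that below-LLQ values were used. They do not restore the order in the tables, mean plots or individual plots.

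**Conclusion.** The point holds in conditional form. The rule can display a change between two below-LLQ values in the wrong direction when a no-number sample is truly the lower one and the reported number is under LLQ/2. Nothing else in the SAP corrects this.

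Its size cannot be derived from the documents. On the assumptions above, the share of true 1.5-fold rises shown as falls runs from 0.1% to 25% at median 0.3 x LLQ, and is zero once the cutoff reaches LLQ/2. A negative displayed mean appears only at median 0.15 x LLQ in the scenarios run, where almost all pairs lie wholly below LLQ.

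The practical reach is low-abundance secondary mediators and possibly the PGDM ratio. Strongly responding TNF-alpha and IL-6, and leukocyte counts, are essentially untouched. This is a rule worth correcting before the displays are produced; it does not cast doubt on the primary cytokine results.

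**What to change.** Use one order-preserving rule within each biomarker. Either option removes the reversals.

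1. Display every below-LLQ result as LLQ/2 in tables and figures, with reported numbers in listings only. Cost: changes wholly below LLQ show as zero and mean change is attenuated, as tabulated above.
2. Keep the reported numbers, and set no-number results to a value no higher than the lowest number reported for that assay. Cost: displays continue to show numbers below the assay's quantification limit, and the substituted value must be stated for each assay.

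The choice between them is a matter of judgement in an exploratory study; mixing them is the problem. With either option, flag affected points in figures, say whether substituted values feed the PGDM criterion in SAP 3.2, and word the BIO_T1 note to say which below-LLQ results were imputed. The change takes a few sentences in the SAP and needs no new data.

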#### 7.1.1. Endpoint / Variables

Challenge	Endpoint
LPS	Time course and magnitude of upregulation of circulating TNF- $\alpha$ and IL-6 as well as urinary tetranor PGDM
GM-CSF	Time course and magnitude of upregulation of circulating total leukocyte numbers.

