### 10.3. Appendix 3: Derived and Transformed Data

#### 10.3.1. General

Multiple Measurements at One Analysis Time Point

 
• Mean of the measurements will be calculated and used in any derivation of summary statistics but if listed, all data will be presented.
 
• If there are two values within a time window the value closest to the target day for that window will be used. If values are the same distance from the target, then the mean will be taken.
 
• Participants having both High and Low values for Normal Ranges at any post-baseline visit for safety parameters will be counted in both the High and Low categories of “Any visit post-baseline” row of related summary tables. This will also be applicable to relevant Potential Clinical Importance summary tables.
 
• For the biomarkers from skin blister fluid, values will be averaged across arms (left and right) for each participant. These averaged values will be used in tables and figures. If one of the values is not collected or is missing, then the single value present in the data will be used in tables and figures. Appropriate footnotes will be provided to reflect data are not an average value.
 

Study Day

 
• Calculated as the number of days from Challenge Administration Date:                             
 
• Ref Date = Missing → Study Day = Missing
 
• Ref Date < Challenge Administration Date → Study Day = Ref Date - Challenge Administration Date
 
• Ref Date ≥ Challenge Administration Date → Study Day = Ref Date - (Challenge Administration Date) + 1
 
 
 

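### Interim tables and figures leave out biomarker values above the ULQ, with no footnote, so any upregulation beyond the assay range is understated there

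*SAP*

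**What the plan says.** This version of the SAP covers dose escalation and the interim analysis only. Section 10.4.2 sets the biomarker rules:

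- **Above the ULQ:** "If any value is above ULQ, such values will be omitted from summaries/figures even if the numeric result is present". The next sentence adds: "These values will only be listed".
- **Below the LLQ:** imputed as half the LLQ if there is no number; "but the numeric result is present, then the numeric values will be used in all displays" if there is one.
- **Failed plate or CV above 20%:** the numeric result is used in all displays.
- **Footnotes:** planned for values below the LLQ, CV above 20% and failed plates. Neither section 10.4.2 nor the table and figure shells in Appendix 8 has one for omitted values above the ULQ.
- **Re-runs:** diluted samples above the ULQ "will be re-run and the new reported values will be used in the final analysis". The interim is not mentioned, and no date is given.

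For LPS, the primary endpoint in section 7.1.1 is "Time course and magnitude of upregulation of circulating" TNF-α and IL-6, with urinary tetranor PGDM. Section 7.1.2 summarises it as absolute values and change from baseline across the time course. The Part II criteria in section 3.2 use each participant's largest increase from baseline at any time point.

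**The concern.** A value above the ULQ is not missing. It is known to be at least as large as the assay's upper limit, and therefore larger than every value left in the display. Deleting it because it is high removes only the top of the distribution. The other three kinds of imperfect result are kept, so nothing offsets the loss. A number from a failed plate is shown while a reading known to be high is not.

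The loss would fall on the time points of strongest upregulation, which is what the primary endpoint describes. There the mean, median and maximum drop. If a participant's highest draw is deleted, his apparent maximum moves to a neighbouring draw. The table shell prints n, so a reader could see that values are absent, but not that they were absent because they were high.

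The review committee receives these displays when it decides on Part II. The Part II rule does not say whether a value above the ULQ counts towards the largest increase.

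**Working it through.** **Inputs**

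- Between-subject SD on the log scale: 0.217 (TNF-α) and 0.394 (IL-6), from Protocol section 10.1. They come from a blister study without a challenge agent.
- n = 4 per challenge agent at the selected dose in Part I (Protocol section 5.1).
- ULQ: not stated. I assume ULQ = c × the median of the values at a given time point and vary c.
- Lognormal values at that time point: my assumption, in line with the protocol's log-scale SDs.

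**Step 1. The plan's own figures.** Protocol Table 1 does not depend on the ULQ rule, but it uses the same SDs. The formula Φ(ln 1.4 / (SD/√n) − 1.2816), one-sided 10%, reproduces it:

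- SD 0.394, n = 4: 0.3365/0.197 − 1.2816 = 0.426, so 66.5% (stated 66%). For n = 8: 87.2% (87%).
- SD 0.434: 60.6% and 81.9% (61%, 82%).
- SD 0.473: 55.6% and 76.7% (56%, 77%).

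**Step 2. Effect of omission on the mean.** With k = ln(c)/s, where s is the log-scale SD, the share omitted is 1 − Φ(k). The displayed mean divided by the true mean is Φ(k − s)/Φ(k).

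Example, s = 0.394:

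- c = 1.0: k = 0, ratio Φ(−0.394)/0.5 = 0.694, a bias of −30.6%.
- c = 1.5: k = 1.029, ratio Φ(0.635)/Φ(1.029) = 0.869, a bias of −13.1%.

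| ULQ as multiple of median (c) | 1.0 | 1.25 | 1.5 | 2.0 |
|---|---|---|---|---|
| SD 0.217: share omitted | 50% | 15% | 3% | 0.1% |
| SD 0.217: bias in mean | −17.2% | −6.7% | −1.9% | −0.1% |
| SD 0.394: share omitted | 50% | 29% | 15% | 4% |
| SD 0.394: bias in mean | −30.6% | −20.4% | −13.1% | −4.9% |
| SD 0.394, n = 4: chance the group maximum is lost, 1 − Φ(k)⁴ | 94% | 74% | 48% | 15% |
| SD 0.394: bias in mean if the ULQ is substituted instead | −19.1% | −10.1% | −5.2% | −1.3% |

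At c = 1.0 there is also a 6% chance (0.5⁴) that all four values are lost and the row shows n = 0. Variability after LPS may exceed these SDs. At an assumed SD of 0.8, the bias in the mean is −57.6% at c = 1.0 and −34.8% at c = 2.0. If no value exceeds the ULQ, the bias is zero.

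**Step 3. Part II rule for LPS.** Enrolment is triggered if at least one participant has a largest increase below 50 pg/mL for TNF-α, below 50 pg/mL for IL-6 and below 1.3 times for PGDM. Omission can only lower a participant's largest retained increase, so it can only push towards enrolment. To change the decision, it would have to leave every retained draw under both 50 pg/mL limits in a participant whose PGDM increase is also below 1.3 times. The schedule has eight post-challenge mediator draws on Session 2 Day 1 alone.

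**The case against.** Much of the case for leaving the rule alone is sound:

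- **The final analysis is protected.** For re-run samples, "the new reported values will be used in the final analysis".
- **The committee is not blind to the values.** Interim material includes listings (section 3.2). Listing 2 covers the primary mediators, and its shell carries a flag for results above the ULQ.
- **Dose escalation used raw data** (section 3.1), so this rule did not touch it.
- **The mean feeds no decision.** The Part II rule works participant by participant, and the interim is descriptive.
- **Exceedance is not shown.** No ULQ is stated. The literature rises in Protocol section 10.1 (42- to 200-fold for TNF-α, 100- to 300-fold for IL-6) were seen at 1 ng/kg of a 10 EU/ng product, that is 10 EU/kg. The selected 0.75 ng/kg at the protocol's 6 EU/ng is 0.75 × 6 = 4.5 EU/kg. A fold-rise also says nothing about exceedance without the assay range.

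These points limit the consequence but do not justify the rule. The SAP itself provides for exceedance, with an omission rule, a re-run rule and a listing flag. The tables and figures would then understate the response without saying so.

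On blister arms, a reader might infer that an arm above the ULQ is dropped and the lower arm alone stands as the participant's average. The documents do not say this. Section 10.3.1 reads: "If one of the values is not collected or is missing, then the single value present in the data will be used". Section 10.4.2 describes missing data as blank fields, which a numeric result above the ULQ is not. The treatment of such an arm is ambiguous, and that is all that can be said.

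**Conclusion.** The rule is wrong for the interim displays. As written, it can only understate the magnitude of upregulation, and no footnote tells the reader. At log-SD 0.394 the mean is about 31% too low with the ULQ at the median and 13% too low at 1.5 times the median. At log-SD 0.217 the figures are 17% and 2%. These rest on a lognormal shape, SDs from unchallenged blisters and an assumed ULQ. The true effect may be zero.

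A reader might go further and conclude that the peak is the primary endpoint and that the trial's primary result is biased downward. The documents do not support that. Peak is one feature of time course and magnitude, no peak variable is tabulated, and re-run values enter the final analysis. Nor do they support the view that the Part II decision is compromised. For LPS, a changed decision needs an unlikely combination in one participant, with the listing overlooked. For GM-CSF, the rule rests on total leukocyte count, for which no ULQ is mentioned. In both arms the error could run only towards enrolling more participants.

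This should be corrected before the interim displays are produced, but it does not threaten the study's conclusions.

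**What to change.** Replace the omission rule in section 10.4.2 for the interim:

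1. Use the diluted re-run value wherever it is available by the interim data cut. For those samples the omission bias is then zero.
2. Otherwise keep the sample in n, median and maximum as a flagged lower bound (≥ULQ), with a footnote giving the count at each time point. Where the median or maximum depends on such a value, print it as a lower bound.
3. Do not present the mean and SD as unbiased when such values are included. Substituting the ULQ reduces the bias but does not remove it (−19.1% against −30.6% at c = 1.0, SD 0.394).
4. State in section 3.2 that a value above the ULQ counts at no less than the ULQ in each participant's largest increase from baseline.
5. State in sections 7.2.2 and 10.3.1 that the same handling applies before blister arms are averaged.

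The cost is SAP wording and some programming. Re-runs may have to be done earlier; the SAP gives no timing, so the laboratory would need to confirm this. No new participants are needed.

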### 3.2. Interim Analyses

Interim Analysis	Details
Study Review Committee	Core GSK members include: 
 
• Study Physician Lead or their delegate; SERM; Statistician; Operations Study Lead; Epigenetics DPU, MM DPU, Scientific Operations Director, Clinical Development Manager.
 

Timing	
 
• At the end of Part I, an interim analysis will be conducted to decide whether to enrol additional participants in Part II of the study, for the optimum dose of 0.75 ng/kg for LPS and 60 ug / m2 for GM-CSF selected in Part I.
 

Biomarker Data Required	
 
• Data for Biomarkers listed in Section 10.3.3 will be presented in tabular and graphical format and summarized descriptively according to GSK's IDSL standards.
 

Statistical Analyses	
 
• There are no planned formal statistical analyses of the data. Descriptive summaries and/or graphical presentations will be presented, including data listings.
 

Criteria for Part II	
If at least one participant meets the criteria below for the optimal dose of 0.75ng/kg for LPS challenge or 60 ug/m2 for GM-CSF challenge, then Part II of the study will be initiated.
 
Participants will be enrolled to Part II – LPS Challenge at the dose level 0.75 ng/kg if for at least one participant:
 
 
• Maximum increase from baseline at any timepoint in plasma level of TNF-<math>\alpha</math> < 50 pg/mL AND
 
• Maximum increase from baseline at any timepoint in plasma level of IL-6 < 50 pg/mL AND
 
• Maximum increase from baseline at any timepoint in urinary tetranor PGDM level < 1.3x
 
 
Participants will be enrolled to Part II – GM-CSF Challenge at the dose level 60 ug/m2 if for at least one participant:
 
 
• Maximum increase from baseline at any timepoint in total leukocyte counts < 5 giga/L
 
• Note: Available data from all biomarkers will be considered before making the decision to move to Part II – GM-CSF Challenge.
 

Part II Decision	
 
• The decision to STOP after Part I or CONTINUE to Part II for each challenge agent will be documented, including any supporting data.
 

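### Interim tables and figures keep results from failed assay plates and drop values above the upper limit of quantification, and the Part II rule does not say how either counts

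*SAP*

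**What the plan says.** SAP 10.4.2 (Handling of Missing Data) sets the biomarker rules.

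- Numeric results flagged for plate failure or CV above 20% "will be used in all displays". The next bullet is the only mitigation: "Appropriate footnotes will be provided in Tables and Summaries to indicate that" below-LLQ, CV-flagged and "Plate Failed Samples have been used". The mock shells in SAP Appendix 8 word this footnote by biomarker.
- For high values: "If any value is above ULQ, such values will be omitted from summaries/figures even if the numeric result is present". The section adds: "These values will only be listed". Diluted samples are to be re-run, with the new values going into the final analysis.

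SAP 3.2 opens the LPS arm of Part II "if for at least one participant" the maximum increase from baseline is below 50 pg/mL for TNF-alpha AND below 50 pg/mL for IL-6 AND below 1.3-fold for urinary tetranor PGDM. The GM-CSF arm uses a maximum leukocyte increase below 5 giga/L. Neither criterion mentions flagged or above-ULQ results.

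**The concern.** A plate that failed QC was rejected by the assay's own acceptance check. Using its numbers needs a reason, and the SAP gives none. High readings are handled the opposite way: a number above ULQ is dropped from the summaries even when it exists.

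The primary LPS endpoint is the time course and magnitude of the cytokine rise, with 4 participants per agent at the selected dose (protocol 5.2). The Part II rule looks at a maximum, in a single participant, against a fixed cut-off. A maximum is sensitive to one bad reading, and with so few people a wrong value is not averaged away. What is at stake is the reported time course and the decision whether to enrol further participants.

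**Working it through.** The plan states no figure on this point, so there is none to reproduce. The check is a reading of the text, then an illustration with assumed inputs.

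**1. Treatment of each kind of result**

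| Result | Summaries and figures | Listings | Repeat assay | Part II maximum (SAP 3.2) |
|---|---|---|---|---|
| Plate failed QC | in, footnoted | in | none planned | not stated |
| CV above 20% | in, footnoted | in | none planned | not stated |
| Above ULQ | out | in | diluted re-run, for the final analysis | not stated |

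**2. Which rule governs the interim.** SAP 5.5 names Appendix 4, which contains 10.4.2, among the handling conventions for interim reporting. SAP 3.2 plans no formal analysis; the committee receives descriptive summaries, graphs and listings. So 10.4.2 is the only stated handling rule for the data behind the Part II decision.

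**3. Logic of the LPS criterion.** A participant counts as a low responder only if all three components are met. A falsely low cytokine reading creates a low responder only if the other two components are already met. A falsely high reading in one cytokine is enough to hide someone who truly meets all three.

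**4. One erroneous reading near the cut-off.** Assumptions: one analyte, one peak sample, baseline 2 pg/mL, lognormal error with the stated CV on the reported level. With s = sqrt(ln(1 + CV²)),

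P(observed rise < 50) = Φ( ln((50 + 2)/(true rise + 2)) / s ).

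For a true rise of 60 at CV 20%: s = sqrt(ln 1.04) = 0.198; ln(52/62) = −0.176; the ratio is about −0.89; P = 0.187. The table gives the probability of landing on the wrong side of 50. The row for 45 is one minus the formula.

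| True rise (pg/mL) | CV 10% | CV 20% | CV 30% | CV 50% |
|---|---|---|---|---|
| 45 (reads 50 or more) | 0.155 | 0.305 | 0.365 | 0.415 |
| 60 (reads below 50) | 0.039 | 0.187 | 0.275 | 0.355 |
| 75 (reads below 50) | 0.000 | 0.024 | 0.091 | 0.203 |
| 100 (reads below 50) | 0.000 | 0.000 | 0.011 | 0.077 |

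These are probabilities for one component, not for opening Part II.

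**5. Omitting values above ULQ.** Assumed rises over nine samples: 0, 0, 1, 5, 20, 45, 300, 180, 30 pg/mL, baseline 2. The levels at the two highest points are 302 and 182.

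- ULQ 100: both are dropped; the displayed maximum is 45, so the below-50 component is met.
- ULQ 200 or 250: only 302 is dropped; the maximum is 180, not met.
- ULQ 500: nothing is dropped; the maximum is 300, not met.

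With the baseline unaffected, omission can only lower the displayed maximum or leave it unchanged. It crosses 50 only if the remaining samples are also low.

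**6. Scope by assay (SAP 10.3.3).** TNF-alpha and IL-6 are MSD assays, tetranor PGDM is LCMS and total leukocytes are flow cytometry. The SAP does not define plate failure or say which assays it covers. The illustration therefore applies to the two MSD components.

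**The case against.** The strongest reply has several parts.

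- **10.4.2 governs displays, not the decision rule.** This stands in part. A reader might infer that failed-plate results are prescribed for the Part II criterion. The SAP does not say so. It is the natural reading because no other rule exists, but it remains an inference.
- **Above-ULQ results are not known to be valid.** This stands. A reader might infer that good data are thrown away, but such values lie outside the quantifiable range, are still listed, and are to be replaced by re-runs in the final analysis. The gap is the interim.
- **Flags are traceable.** Largely right. Listing shells BIO_L1 and BIO_L2 have a row-level Test Comments column, and these listings are interim deliverables. The shell entries show LLQ, CV and ULQ flags but no plate-failure flag. In tables and figures the footnote identifies only the biomarker.
- **One flipped cytokine does not open Part II.** Correct, because of the AND. Nor is the GM-CSF criterion shown to be affected: it uses flow cytometry, and all available biomarkers are to be considered before that decision.
- **The error example does not isolate flagged data.** Fair. A sample at CV 20% carries no flag, so the 19% at that point is ordinary noise against a hard cut-off. The extra harm from CV-flagged data is the move from there to 28% at CV 30% or 36% at CV 50%. The error on a failed plate is unknown.
- **Exclusion has its own risk.** Also fair. With 4 participants, dropping a plate could remove a baseline, which SAP 5.2 then sets to missing, or a peak, which pushes towards the Part II trigger.

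The study is exploratory and tests no hypotheses (SAP 2.4), and a later plan will cover final reporting. That lowers the stakes, but it gives no reason to summarise failed-plate results with no comparison display.

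**Conclusion.** The point holds as a cheap improvement to the interim plan. The use of failed-plate and CV-flagged results in all displays, without repeat or comparison, is stated outright. So is the omission of above-ULQ values from summaries and figures. How either counts in the Part II maximum is left unsaid.

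The size is modest and depends on how close a participant lies to 50 pg/mL. Under the assumed error model, misreading one component is a real possibility at a true rise of 60 and small at 100, where it reaches 8% only at CV 50%. The baseline, error distribution, ULQ values and time profile are all assumptions.

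A reader might also infer that one failed plate supplies a quarter of the data in an arm. That would require all of one participant's samples to share a plate, and the documents give no plate layout.

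**What to change.** In SAP 10.4.2 and 3.2:

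1. Show the primary LPS cytokine summaries, mean plots and Part II classification with and without failed-plate and CV-above-20% results. Leave failed-plate results out of the main version and replace them by a repeat assay where sample remains.
2. Mark flagged points individually on the individual plots, and add plate failure to the entries in the listing Test Comments column.
3. At the interim, use the diluted re-run value for any above-ULQ sample, or count it as at least ULQ when deriving the maximum increase.

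The cost is SAP wording, one extra set of interim outputs, and any repeat assays. Where no sample remains, some values will be missing from the main version, possibly a baseline or a peak; the with/without display shows what difference that makes.
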